- Grade ≥ 3 total bilirubin or hepatic transaminase (aspartate aminotransferase [AST] and alanine aminotransferase [ALT]) elevations that return to ≤ Grade 1 (if normal at study entry) or ≤ baseline values within 7 days of interrupting study drug;
- Note: Allergic reactions that necessitate discontinuation of study drug will not be considered a DLT;
- Grade ≥ 3 symptomatic fasting hyperglycemia (e.g., dehydration or acidosis requiring hospitalization);
- Grade ≥ 4 fasting hypercholesterolemia or triglyceridemia for ≥ 14 days despite intervention with a lipid-lowering agent:
- Grade ≥ 4 thrombocytopenia;
- Grade 3 thrombocytopenia that lasts ≥ 7 days or is associated with clinically significant bleeding;
- Grade ≥ 4 neutropenia (absolute neutrophil count < 500/µL) lasting ≥ 7 days or accompanied by fever (oral or tympanic temperature ≥ 38.0°C [100°F]);
- Grade ≥ 3 total bilirubin or hepatic transaminase (ALT or AST) elevations that do not return to ≤ Grade 1 (if normal at study entry) or ≤ baseline values within 7 days of interrupting study drug;
- For patients with Gilbert's disease and with Grade 2 bilirubin at baseline, total bilirubin $\ge 10 \text{ x}$ the upper limit of normal (ULN) will be considered a DLT:
- Bradycardia Grade ≥ 2;
- Myocardial ischemia Grade ≥ 2;
- Mucositis/stomatitis Grade 3 not responding to standard-of-care therapy or Grade 4;
- Decrease in left ventricular ejection fraction (LVEF) to ≤ 45%;
- Increase of QTc to ≥ 500 msec or by 60 msec;
- Pneumonitis Grade ≥ 2.

After determination of the MTD, patients continue to receive their protocolassigned dose level of GDC-0084 until progression of their disease or an unacceptable toxicity, whichever occurs first.

Sponsor: Kazia Therapeutics Limited Version: Amendment 4 Date: 31 Mar 2020

Protocol Number: NVGN-0084-201

IND Number: 112,608

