Protocol Number: NVGN-0084-201 Version: Amendment 4 IND Number: 112,608

Dose-Escalation Rules

Dose-escalation will occur in Stage 1:

The initial dose (Dose Level 0) for QD MTD determination in will be 60 mg. Dose levels will increase in 15 mg steps:

- The dose-escalation portion of the study (Stage 1) will use a "3 + 3" design to assess the safety, tolerability, and PK of GDC 0084 administered orally in 28-day cycles:
- Each dose cohort will initially enroll 3 patients. If none of these patients experiences a DLT within the DLT assessment period (Day 1 - 28), escalation will proceed to the next higher dose level by opening the next higher dose cohort with newly recruited patients;
- If 1 patient experiences a DLT, the cohort will be expanded until a second patient experiences a DLT or to a maximum of 6 patients. When a second patient has a DLT, the MTD is determined as 1 dose level below the current dose level; i.e. the highest dose level at which less than 1/3 of patients (e.g. 1 of 6) experiences a DLT will be declared the MTD.
- If 2 or more patients experience a DLT at Dose Level 0, the MTD will be declared at 45 mg, which was the MTD established in the previous phase I study in patients with advanced glioma with a QD dosing schedule.

On the basis of the review of real-time safety data and available preliminary PK data from this study with GDC-0084, dose-escalation may be halted or modified by the sponsor as deemed appropriate.

Decisions regarding dose-escalation and selection will be made by a CRC including the medical monitor, recruiting Investigators, sponsor representative and any other relevant and necessary expert on as needs basis, according to the CRC charter.

Definition of Dose Limiting Toxicity

All AEs, including DLTs, will be reported, with severity assessed according to National Cancer Institute (NCI) Common Terminology Criteria for Adverse Events (CTCAE), version 4.03. In case a patient experiences one of the below, study participation will be terminated for this patient and the EoT visit should be performed.

For dose-escalation purposes, DLT assessments will be performed by the sponsor in consultation with the Investigators during the CRC meetings.

A DLT is defined as any one of the following toxicities occurring within the DLT assessment window (Cycle 1, Days 1 - 28) and assessed by the Investigator to be probably or possibly related to GDC-0084:

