- Grade ≥ 3 non-hematologic or non-hepatic toxicity that is not related to hyperglycemia or hyperlipidemia or mucositis/stomatitis and is not due to disease progression or another clearly identifiable cause, excluding the following:
 - Alopecia of any grade;
 - Grade 3 fever or Grade 4 fever < 5 days duration;
 - Grade 3 infection < 5 days duration or that responds to treatment;
 - Grade 3 weight gain or loss;
 - Grade 3 diarrhea lasting less than 5 days or that responds to standard-of-care therapy including hospitalization;
 - Grade 3 nausea or vomiting, in the absence of premedication, that lasts for less than 48 hours or responds to standard-of-care therapy:
 - Grade 3 or asymptomatic Grade 4 electrolyte imbalance that resolves or improves within 7 days with or without medical intervention, including hospitalization;
 - Grade 3 or 4 serum amylase or lipase or creatine phosphokinase laboratory abnormality that is asymptomatic (without other laboratory evidence suggestive of pancreatitis, rhabdomyolysis, or other major organ dysfunction) and returns to baseline within 7 days of interrupting study drug;

Version: Amendment 4 Date: 31 Mar 2020

Protocol Number: NVGN-0084-201 IND Number: 112.608

o Grade ≥ 3 total bilirubin or hepatic transaminase (aspartate aminotransferase [AST] and alanine aminotransferase [ALT]) elevations that return to ≤ Grade 1 (if normal at study entry) or ≤ baseline values within 7 days of interrupting study drug:

- Note: Allergic reactions that necessitate discontinuation of study drug will not be considered a DLT:
- Grade ≥ 3 symptomatic fasting hyperglycemia (e.g., dehydration or acidosis requiring hospitalization):
- Grade ≥ 4 fasting hypercholesterolemia or triglyceridemia for ≥ 14 days despite intervention with a lipid-lowering agent;
- Grade ≥ 4 thrombocytopenia;
- Grade 3 thrombocytopenia that lasts ≥ 7 days or is associated with clinically significant
- Grade ≥ 4 neutropenia (absolute neutrophil count < 500/µL) lasting ≥ 7 days or accompanied by fever (oral or tympanic temperature ≥ 38.0°C [100°F]);
- Grade ≥ 3 total bilirubin or hepatic transaminase (ALT or AST) elevations that do not return to ≤ Grade 1 (if normal at study entry) or ≤ baseline values within 7 days of interrupting study drug:
- For patients with Gilbert's disease and with Grade 2 bilirubin at baseline, total bilirubin ≥ 10 x upper limit of normal (ULN) will be considered a DLT;
- Bradycardia Grade ≥ 2;
- Myocardial ischemia Grade ≥ 2;

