4.2 Eligibility Criteria

4.2.1 **Inclusion Criteria**

Patients must meet all the following inclusion criteria to be eligible for enrollment into the study:

- 1) Signed informed consent approved by the Institutional Review Board (IRB). Patients must sign an authorization for the release of their protected health information;
- 2) Age ≥ 18 years;
- 3) Life expectancy > 12 weeks;
- 4) Present with histologically confirmed intracranial (supratentorial) unmethylated MGMT promotor status GBM (WHO Grade IV astrocytoma) with an MGMT status that has been confirmed by validated PCR or validated alternative genomic analysis;
- 5) Have undergone maximal or subtotal surgical resection of their tumor and within 6 weeks of surgery commenced radiation and then received at least 75% of planned treatment with XRT/TMZ or XRT only (if clinically indicated), which consists of XRT by external beam to a partial brain field in daily fractions of 2.0 Gray (Gy), to a planned total dose to the tumor of 60.0 Gy, in conjunction with TMZ oral QD 75 mg/m² in accordance with the Stupp regimen;
- 6) Karnofsky Performance Status (KPS) ≥ 70;
- 7) Cranial magnetic resonance imaging (MRI) must have been performed within 14 days prior to or on the day of the Enrollment/Week 1 Visit;
- 8) Stable or decreasing corticosteroid dose within 7 days prior to the first dose;
- 9) Adequate bone marrow/hematological function within 14 days prior to Day 1:
 - White blood cell count (WBC) > 3,000/µL, absolute neutrophil count > 1,500/mm³;
 - Platelet count of > 100,000/mm³;
 - Hemoglobin > 10 mg/dL;
 - Eligibility level for hemoglobin may be reached by transfusion;
- 10) Adequate liver function within 14 days prior to Day 1:
 - Total bilirubin ≤ 1.5 x ULN;
 - AST and ALT ≤ 2.5 x ULN;
- 11) Adequate renal function within 14 days prior to Enrollment/Week 1 Visit:
 - Creatinine ≤ 1.5 mg/dL;
 - Urine dipstick for proteinuria < 2+. Patients discovered to have ≥ 2+ proteinuria on dipstick urinalysis should undergo a 24-hour urine collection and must demonstrate ≤ 1.0 g of protein in 24 hours: OR
 - Urine protein/creatinine ratio ≤ 1.0;
- 12) International normalized ratio (INR) or prothrombin time (PT) (secs) and activated partial thromboplastin time (aPTT) within 7 days prior to Enrollment:
 - ≤1.5 x ULN (except for patients receiving anticoagulation therapy) in the absence of therapeutic intent to anti-coagulate the patient;

Version: Amendment 4 Date: 31 Mar 2020

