4.4 Study Interventions

4.4.1 **Treatment Schedule**

Prior to Screening

Version: Amendment 4 Date: 31 Mar 2020

Protocol Number: NVGN-0084-201 IND Number: 112.608

All patients will receive concomitant XRT/TMZ or XRT delivered as fractionated focal irradiation in daily fractions of 2 Gy given 5 days per week for 6 weeks, for a total of 60 Gy, with concomitant administration of daily oral TMZ 75 mg/m²/day from the first day to the last day of radiotherapy.

Patients must have recovered from side effects of this therapy to at least baseline or Grade 1 before entering the study. Lymphopenia and/or alopecia may be Grade 2 if clinically indicated in the judgement of the investigator.

After Screening/Enrollment

After screening, in Stage 1, the initial cohort will receive an oral dose of 60 mg GDC-0084 QD (4 x 15 mg capsules). Patients of future cohorts are planned to receive GDC-0084 at increasing levels with 15 mg steps according to the dose-escalation rules until disease progression or an unacceptable toxicity, whichever occurs first.

For the Stage 2 expansion, patients will receive doses of oral GDC-0084 at the RP2D established from Stage 1 for QD dosing in 28-day cycle until disease progression or an unacceptable toxicity, whichever occurs first.

Fed and Fasted Instructions

Days	C1D1 and C2D1 only	All other days
	(i.e. just 2 days in total)	
Fed Arm	On days C1D1 and C2D1 ONLY, patients allocated to the fed arm should consume a high-fat, high-calorie meal approximately 30 minutes prior to dosing , and should then refrain from eating for at least 4 hours post-dose. The high-fat (approximately 50 percent of total caloric content of the meal) and high-calorie (approximately 800 to 1000 calories) meal should derive approximately 150, 250, and 500-600 calories from protein, carbohydrate, and fat, respectively.	Patient can follow their own normal diet, which ideally should remain as consistent as possible,
	Example of the meal is two eggs fried in butter, two strips of bacon, two slices of toast with butter, four ounces of hash brown potatoes and eight ounces of whole milk. Alternatively, for vegetarians, beans, peas, tofu and cheese are good sources of protein and fat that satisfy protocol criteria.	and; Capsules must be taken 1 hour before food or 2 hours after food, as stated in Diary.

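### The hepatic DLT rule grants the Grade 1 recovery target only to patients normal at entry, so an eligible patient with a mildly raised baseline can be a DLT at a lower residual value than a normal-entry patient who is not (rare, conservative, low priority)

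*Combined protocol and SAP*

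**What the plan says.** The DLT list in Section 3.7.1 makes a related Grade 3 or higher elevation of bilirubin, AST or ALT in Cycle 1 a DLT when values "do not return to ≤ Grade 1 (if normal at study entry) or ≤ baseline values within 7 days of interrupting study drug". The synopsis (Section 2.1) has the same condition: "elevations that do not return to ≤ Grade 1 (if normal at study entry", closing the parenthesis and continuing identically. In both places a matching carve-out under the non-hematologic bullet repeats the two-part target in mirror form.

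Patients with mildly raised values may enter. Section 4.2.1, criterion 10, sets the limits at "Total bilirubin ≤ 1.5 x ULN" and "AST and ALT ≤ 2.5 x ULN". Section 4.4.1 requires that patients have "recovered from side effects of this therapy to at least baseline or Grade 1 before entering the study", so residual Grade 1 effects of chemoradiation are acceptable.

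Two other items in the DLT list bear on the reading. The Gilbert's bullet applies only to patients with that "disease and with Grade 2 bilirubin at baseline". The amylase, lipase and creatine phosphokinase exclusion requires that the value "returns to baseline within 7 days of interrupting study drug", and asks this of every patient whatever the entry value.

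DLT occurrence is the primary endpoint (Section 4.5.1), and the escalation rule is: "When a second patient has a DLT, the MTD is determined as 1 dose level below the current dose level".

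**The concern.** The parenthesis attaches to the Grade 1 limb alone. A patient who was not normal at entry is left with only the baseline limb. When that baseline lies between the ULN and the Grade 1 ceiling, this patient's limit is lower than the one for a patient who entered normal. Two patients with the same kind of event can then be classified in the wrong order: the one with less residual abnormality is the DLT.

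What is at stake is the DLT count. One such call turns a 0-of-3 cohort into an expansion toward 6. Together with one other DLT in the same cohort, it sets the MTD one level lower, or at 45 mg if it happens at the 60 mg starting level.

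**Working it through.** The documents state no figure that depends on this rule, so there is nothing to reproduce. The check has three parts.

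**1. The rule as worded.** Let *b* be the entry value, *v* the value 7 days after interruption, and *c* the upper limit of Grade 1, all in multiples of ULN. After a related Grade 3 or higher event, the patient is not a DLT if (*b* ≤ 1 and *v* ≤ *c*) or *v* ≤ *b*; otherwise the patient is a DLT. The protocol grades by CTCAE 4.03 but does not print its limits, so *c* is an assumption: 2.0 to 3.0 for AST/ALT and 1.5 for bilirubin.

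| Test | Entry *b* | Day 7 *v* | Ratio *v/b* | DLT? |
|---|---|---|---|---|
| ALT, raised entry | 1.1 | 1.3 | 1.2 | Yes |
| ALT, normal entry | 0.9 | 2.0 | 2.2 | No |
| Bilirubin, raised entry | 1.2 | 1.3 | 1.1 | Yes |
| Bilirubin, normal entry | 1.0 | 1.5 | 1.5 | No |

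The ALT pair gives the same result for *c* = 2.0, 2.5 and 3.0. The order is wrong both in absolute value and relative to baseline.

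**2. Width of the affected band.** The normal-entry limit exceeds the raised-entry limit by max(*c* − *b*, 0):

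| Analyte, assumed *c* | Entry values *b* | Gap (x ULN) |
|---|---|---|
| AST/ALT, 3.0 | 1.1, 1.5, 2.0, 2.5 | 1.9, 1.5, 1.0, 0.5 |
| AST/ALT, 2.5 | 1.1, 1.5, 2.0, 2.5 | 1.4, 1.0, 0.5, 0 |
| AST/ALT, 2.0 | 1.1, 1.5, 2.0, 2.5 | 0.9, 0.5, 0, 0 |
| Bilirubin, 1.5 | 1.1, 1.3, 1.5 | 0.4, 0.2, 0 |

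The gap exists wherever the baseline is above ULN and below the Grade 1 ceiling.

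**3. How often, and with what effect.** All rates are assumed; the documents give none. Per-patient probability of such a call: *a* = (share with raised baseline) × (related Grade 3 or higher hepatic event in Cycle 1) × (share of those within Grade 1 but above baseline at day 7). The chance of at least one among *n* patients is 1 − (1 − *a*)^*n*. Section 6.4 plans about 12 Stage 1 patients, range 6 to 24.

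| Inputs | *a* | *n* = 6 | *n* = 12 | *n* = 24 |
|---|---|---|---|---|
| 20% × 3% × 37.5% | 0.00225 | 1.3% | 2.7% | 5.3% |
| 20% × 3% × 75% | 0.0045 | 2.7% | 5.3% | 10.3% |

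For 12 patients, all-low inputs (10% × 1% × 50%) give 0.6% and all-high inputs (30% × 5% × 100%) give 16.6%. The latter multiplies three extremes; replacing its 100% with 50% gives 8.6%.

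For one cohort with probability *p* of any other DLT per patient, the chance of escalating is E(*p*) = (1 − *p*)³ + 3*p*(1 − *p*)⁵, taking 1 of 6 as permitting escalation. With the extra calls, and assuming independence, *p* becomes 1 − (1 − *p*)(1 − *a*).

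| *p* | E(*p*) | with *a* = 0.00225 | with *a* = 0.0045 |
|---|---|---|---|
| 0.10 | 90.6% | 90.3% (fall 0.33 points) | 89.9% (fall 0.67) |
| 0.20 | 70.9% | 70.5% (fall 0.39) | 70.1% (fall 0.78) |
| 0.30 | 49.4% | 49.1% (fall 0.32) | 48.8% (fall 0.64) |

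The fall is below 0.1 points with all-low inputs and 2.1 to 2.6 points with all-high inputs.

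**The case against.** The strongest defense is that the rule is deliberately cautious. A patient who enters with an already abnormal liver has less reserve, and full return to baseline after a severe related event is a reasonable demand. Return to baseline is also what the list asks for amylase, lipase and creatine phosphokinase, and the trial starts at 60 mg, above the phase 1 MTD of 45 mg. Every misclassification under the current wording adds a DLT, which is the safe direction.

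The direction of the error is conceded. The rationale is possible, but the protocol does not state it, and it does not account for the ordering: the patient who passes is worse both in absolute value and in fold-change from baseline. The pancreatic and muscle enzyme exclusion is uniform across patients; the hepatic one is not. Section 4.9.1 also treats AST/ALT up to 2.5 x ULN as fit for the next cycle whatever the baseline.

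Three further limits stand:

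- **Frequency.** No hepatic event appears among the phase 1 DLTs or most frequent related AEs listed in the Risk/Benefit Analysis (47 patients). Nothing in the documents supports any particular partial-recovery share, hence the range from 37.5% to 75%.
- **Review.** The sponsor assesses DLTs with the Investigators at Cohort Review Committee (CRC) meetings, so each case is looked at. No text, however, lets them change the recovery target.
- **Participation.** A reader might infer that the wording costs such patients their place in the study, since Section 3.7.1 ends participation after a DLT by default. The documents do not support that in general. The same section lets the Investigator and medical monitor agree to continue after a reversible DLT. For bilirubin that stays raised, Section 4.9.1 requires a value within normal limits before the next cycle, so that patient is barred whether or not a DLT is called.

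**Conclusion.** The rule is wrong as written, at low priority. That an eligible raised-baseline patient can be a DLT at a lower residual value than a normal-entry patient who is not follows from the wording alone. It needs only a baseline above ULN and below the Grade 1 ceiling. The matching carve-out, the Gilbert's bullet and Section 4.11.2 (which refers back to 3.7.1) give no relief.

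The consequence to claim is the DLT count and the 3+3 decision. On the assumed inputs the chance of at least one such call is about 3% to 5% among 12 patients, and one cohort's escalation probability falls by about 0.3 to 0.8 points. These figures indicate scale only, because every rate behind them is assumed, including how common raised baselines are.

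A reader might infer that the MTD is unreliable or that patients are exposed to excess risk. Neither follows. Lowering the MTD also needs another DLT in the same cohort, and the error leads toward a lower dose, not a higher one.

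**What to change.** In the hepatic DLT bullet and its matching carve-out, in both the synopsis and Section 3.7.1, state the target as: *return to ≤ Grade 1, or to ≤ baseline if baseline is above Grade 1, within 7 days of interrupting study drug* (negated in the DLT bullet). Under this wording neither raised-entry example above is a DLT, and normal-entry patients are unaffected. The baseline limb stays for a pre-dose value that has risen above Grade 1 since screening.

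The cost is one line changed in four places. The downside is that partial recovery within Grade 1 from a raised baseline no longer counts as a DLT, as is already so for normal-entry patients. If the sponsor does intend a stricter standard for raised-baseline patients, it should say so and give the reason. Requiring return to baseline from everyone is not recommended: a day-7 value inside the normal range but slightly above baseline would then be a DLT.
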